Hypothesis: Loteprednol 0.5% gel will perform similarly or better than a regimen of prednisolone acetate 1% and fluorometholone 0.1% in the prevention of visually significant postoperative corneal haze after photorefractive keratectomy (PRK) with a lower incidence of intraocular pressure elevation.

Objectives: We aim to conduct a prospective, randomized trial to compare the incidence of intraocular pressure rise and visually significant postoperative corneal haze after PRK with the use of loteprednol 0.5% gel compared to the use of earlier generation steroids, prednisolone acetate 1% suspension and fluorometholone 0.1% suspension.

Patients undergoing PRK will be assigned to 1 of 2 postoperative steroid regimens. Group 1 will use only loteprednol 0.5% gel, tapered off slowly based on clinical evaluations of the corneal healing response. Group 2 will use prednisolone acetate 1% suspension tapered down to a regimen of fluorometholone 0.1% which will then be tapered off based on clinical evaluations of the corneal healing response. If no difference in efficacy or safety is detected between these two regimens, this study will support the use of either steroid regimen in patients after PRK. If there is a major difference in the efficacy or safety of these two regimens, this could influence post-refractive surgery treatment practices.

7. Is this a multi-site study, where more than one site needs IRB approval?

Yes No

8. Background and Introduction:

In photo-ablation procedures, an excimer laser is used to sculpt corneal tissue to correct refractive error. During PRK, the surface epithelium is removed and the laser energy is applied to reshape the underlying corneal stroma. This procedure is FDA approved and used widely. Corneal haze is a well known and a potentially vision threatening postoperative complication of PRK. Topical ophthalmic corticosteroids are routinely prescribed by most surgeons postoperatively to help prevent this complication.

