Prior to surgery, patients will be randomly assigned to one of two postoperative steroid regimens. Group 1 will use loteprednol 0.5% gel in both eyes, starting at a frequency of four times per day for the first week and then tapered off based on clinical judgement of the corneal healing response. Group 2 will use prednisolone acetate 1% suspension in both eyes, starting at a frequency of four times per day for the first week, then tapered down to a regimen of fluorometholone 0.1% suspension, which will then be tapered off based on clinical judgement of the corneal healing response.

All surgical procedures will be performed according to the standard of care and the surgeons' standard practices. The study outcome measures are standard of care for pre-operative and post-operative evaluation of refractive surgery patients.

The primary outcome measure will be intraocular pressure at each study time point. Secondary outcomes will be grade of corneal haze, manifest refraction, best corrected visual acuity, and uncorrected visual acuity.

Study outcome measures will be evaluated for each treated eye of each subject at each study time point. Routine clinical management may be altered if the intraocular pressure is elevated sufficiently to require medical intervention, if there is significant postoperative corneal haze, or if there are other postoperative complications. In these situations, additional IOP lowering drops may be added or the steroid decreased, changed, or increased, based on the clinical picture and physician judgement. Additional examinations between study time points may be performed as necessary according to the surgeon's usual care, but will not be considered part of the study data. Patients have the right to withdraw at any time and future medical care will not be influenced by their lack of participation.

If enhancement surgery is deemed necessary and performed during the one-year post-operative period, study data collection will end for that eye at the time of the enhancement. All prior data collected will still be included in the statistical analysis and if only one eye requires enhancement, data collection will continue on the fellow eye until the last planned study time point.

Eyes will be evaluated with the following procedures:

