- Intraocular pressure (by applanation tonometry): Pre-operatively and post-operative week 1 (\pm 3 days), month 1 (\pm 10 days), month 2 (\pm 10 days), month 3 (\pm 14 days), month 6 (\pm 1 month), and month 12 (\pm 1 month)

Note: Intraocular pressure will be measured by a technician or physician who is masked to the treatment regimen of the patient at each visit.

- Grade of corneal haze (Fantes scale): Post-operative Month 1 (\pm 10 days), month 2 (\pm 10 days), month 3 (\pm 14 days), month 6 (\pm 1 month), and month 12 (\pm 1 month)

Note: Corneal haze will be graded by a study physician who did not perform the original surgery and is masked to the treatment regimen of the patient at each visit.

- Manifest refraction (sphere, cylinder, and axis): Pre-operatively and post-operatively month 1 (\pm 10 days), month 2 (\pm 10 days), month 3 (\pm 14 days), month 6 (\pm 1 month), and month 12 (\pm 1 month)

- Best corrected visual acuity: Pre-operatively and post-operatively month 1 (\pm 10 days), month 2 (\pm 10 days), month 3 (\pm 14 days), month 6 (\pm 1 month), and month 12 (\pm 1 month)

- Uncorrected visual acuity: Pre-operatively and post-operative day 1 (\pm 1 day), week 1 (\pm 3 days), month 1 (\pm 10 days), month 2 (\pm 10 days), month 3 (\pm 14 days), month 6 (\pm 1 month), and month 12 (\pm 1 month)

- Pupil size measured in the dark: Pre-operatively only

- Corneal pachymetry: Pre-operatively only

Data and Safety Monitoring:

There is no formal data and safety monitoring board for this study. All treatments, procedures, and testing being performed in the study are within the standard of care and treatment for PRK patients. This study does not put study participants at any known increased risk beyond that normally assumed by patients undergoing PRK outside the study. The investigators feel that the standard processes for identifying and reporting adverse events (AE) are sufficient to safeguard the well-being of study participants.

The investigators have a nomogram from which they work and therefore have expected vision outcomes for patients on an individual basis. It is routine practice to compare actual with expected outcomes as a quality assurance measure. Should any concerns arise prior to completion of the study, a safety analysis will be conducted immediately.

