For this protocol, an AE is any "on study" untoward medical occurrence (e.g., sign, symptom, disease, syndrome, intercurrent illness) that is experienced by a study subject, regardless of the suspected cause. Both serious and non-serious AEs will be graded on a three-point scale (mild, moderate, severe), and the investigators will assess whether there is a reasonable possibility that study procedure caused or contributed to the AE.

Adverse events that start on Day 0 (Surgery) through the last study visit will be recorded on the study AE log and described in detail in the patient chart. Subjects discontinued early from the study due to an adverse event will be asked to return for a final evaluation. All study-related adverse events will be followed until resolution (or determined to be irreversible, chronic, or stable).

Adverse events that are determined to be unexpected, possibly related to the study procedure, and place subjects at increased risk, will be reported to the Institutional Review Board (IRB) according to their guidelines.

Standard of Care / Research Costs:

All procedures are considered within the standard of care for PRK surgery and will be billed to patients in the usual manner; however, participants will be eligible for a reduced study fee for their surgery and post-operative care. PRK surgery is considered cosmetic surgery and is never billed to insurance. The refractive surgery charge includes standard post-operative examinations up to one year.

Loteprednol 0.5% gel is not available in a generic formulation and is therefore significantly more expensive than generic prednisolone acetate 1% suspension and fluorometholone 0.1% suspension. A request for a donation of loteprednol 0.5% gel for this study has been submitted to Bausch and Lomb and is currently under review. If approved, this drug donation will allow us to eliminate the additional expense of a branded drug for patients that are randomized to the loteprednol group.

If enhancement surgery is deemed necessary during the one-year post-operative period, this will be included based on the patient's initial fee, as is standard of care. Any other costs related to management of adverse events, or if additional refractive correction is necessary at some time after the one-year postoperative period, will remain the patient's responsibility and are not included in the study surgery fee.

7. Are all procedures for research purposes only (non-standard or non-standard of care procedures)?

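### The objective is haze incidence, but the plan summarises haze grade visit by visit and does not count steroid changes made for haze by arm

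*Combined protocol and SAP*

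**What the plan says.** - **Objectives.** The trial will "compare the incidence of intraocular pressure rise and visually significant postoperative corneal haze after PRK" between the two regimens. The same part gives the reading of a null result: "If no difference in efficacy or safety is detected between these two regimens, this study will support the use of either steroid regimen". Section 6, item 2 repeats this in substance.
- **Section 4, item 6, outcomes.** Intraocular pressure (IOP) at each time point is primary. "Secondary outcomes will be grade of corneal haze, manifest refraction, best corrected visual acuity, and uncorrected visual acuity".
- **Item 6, treatment.** Both regimens include a discretionary taper. Loteprednol, after its first week, is "tapered off based on clinical judgement of the corneal healing response", and the fluorometholone phase of Group 2 is handled the same way. Separately, management may be altered for raised IOP, significant haze or other complications: "additional IOP lowering drops may be added or the steroid decreased, changed, or increased, based on the clinical picture and physician judgement". Extra examinations are allowed, "but will not be considered part of the study data".
- **Item 6, measurement.** Haze is graded on the Fantes scale at months 1, 2, 3, 6 and 12. "Corneal haze will be graded by a study physician who did not perform the original surgery and is masked to the treatment regimen". Best corrected acuity is measured at the same five visits. No Fantes grade is named as visually significant.
- **Item 6, safety monitoring.** "Adverse events that start on Day 0 (Surgery) through the last study visit will be recorded on the study AE log". Events are graded mild, moderate or severe. No table by arm is described.
- **Item 9.** The study variables are IOP, haze grade, refraction and the two acuities, described with standard statistics at the scheduled time points. Steroid changes are not on the list. Data after enhancement surgery are dropped. The sample size concerns IOP elevation only; no haze rate, test or margin appears.

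**The concern.** Incidence asks how many patients ever developed visually significant haze. A summary of grade at each visit tells how many have it on that day. Haze can appear and clear, on its own or because the steroid was increased or switched, so the two quantities can differ.

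The taper belongs to both assigned regimens and raises no difficulty. A steroid change made because haze has become significant goes beyond the taper, and later grades carry its effect. If one arm needed more such changes, the per-visit grades could still look alike, and no planned table would show the difference.

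This matters because the documents treat an undetected difference as support for either regimen. Similar grades after uncounted rescue could then be read as equal prevention.

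**Working it through.** **1. Objective against analysis.** The objective names incidence. Item 6 defines the outcome as grade, and item 9 summarises it by visit. No stated step turns the five grades into one per-patient result, although the masked grades would supply it. Steroid changes for haze are in neither the outcome list nor the variable list.

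**2. The plan's own figure.** The only sample size is for IOP elevation, 1.95% v 7.48%, alpha 0.05, power 80%. With pooled variance, two-sided, and mean proportion 0.04715:

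n = [1.96·√(2·0.04715·0.95285) + 0.8416·√(0.0195·0.9805 + 0.0748·0.9252)]² / 0.0553² ≈ 229.4, so 230 per arm, 460 in total.

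This matches the 460 stated, counted as eyes. It says nothing about haze.

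**3. Prevalence against cumulative incidence.** Every rate in this step is assumed; none is in the documents. Let p be the proportion ever hazy, w_k the share of onset at visit k, and c the share cleared by the next scheduled visit, with no later clearing or relapse.

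Prevalence at visit k = p·[w_k + (1−c)·(sum of earlier w)].

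With onset spread evenly over months 1, 2, 3 and 6 (w = 0.25 each) and equal clearing in both arms, the share of the incidence difference that is visible is 0.25 + 0.75(1−c) at month 6, the largest of any visit, and 1−c at month 12.

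| c | Month 6 share | Month 12 share | Month 6 difference if 10% v 5% ever hazy |
|---|---|---|---|
| 0 | 100% | 100% | 5.0 points |
| 0.4 | 70% | 60% | 3.5 points |
| 0.7 | 47.5% | 30% | 2.4 points |
| 0.9 | 32.5% | 10% | 1.6 points |

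These shares depend on the assumed profile:
- Onset 10/60/20/10% over the same four visits: the largest share is at month 2, 0.60 + 0.3·0.10 = 63% at c = 0.7, and 0.60 + 0.1·0.10 = 61% at c = 0.9.
- Onset 70/15/10/5%: month 1 shows 70% at either value of c.
- All onset at one visit: that visit shows the full difference.
- Under equal clearing the 2:1 ratio is unchanged throughout.

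The direction depends on equal clearing. With even onset and 10% v 5% ever hazy, at month 6:
- Clearing 40% in the hazier arm and 90% in the other: 10·0.70 − 5·0.325 = 7.0 − 1.625 = 5.4 points, more than the true 5.
- The reverse: 10·0.325 − 5·0.70 = 3.25 − 3.5 = −0.25 points.

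**4. Precision of a per-patient comparison.** One outcome per patient, 125 per arm (in brackets 115, half of the 230 patients in item 9). 95% CI = d ± 1.96·√{[p1(1−p1) + p2(1−p2)]/n}. Power is two-sided at 0.05 with pooled null variance. For 10% v 5% with n = 125, the half-width is 1.96·√(0.1375/125) = 6.5 points.

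| Assumed ever-haze | Difference | 95% CI | Power |
|---|---|---|---|
| 4% v 2% | 2 points | −2.2 to 6.2 (−2.4 to 6.4) | 15% (14%) |
| 10% v 5% | 5 points | −1.5 to 11.5 (−1.8 to 11.8) | 32% (30%) |
| 20% v 10% | 10 points | 1.2 to 18.8 (0.9 to 19.1) | 60% (57%) |

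**5. What scheduled grades still miss.** If a share u of cases is first treated between visits and a share c of those clears before the next grade, the observed proportion is p(1−uc). With u = 0.25 and c = 0.7 (assumed), 10% v 5% is seen as 8.25% v 4.1%.

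**The case against.** Item 9 is a form field asking for a summary of methods. It does not rule out a per-patient haze summary, and the masked grades for one are already collected. That stands: what is missing is a stated derivation, and the unnamed Fantes threshold is in itself only missing detail.

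Allowing the steroid to be changed is ordinary care. That also stands. Comparison by assigned arm is right, and the per-visit grades are a legitimate treatment-policy result. A reader might infer that they are invalid or that management should be restricted; nothing in the documents supports either.

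Significant haze needing a steroid change plausibly qualifies as an adverse event, so a table could be built later from the log and charts. This holds in part. Complete capture of each change is not assured, the log's severity scale is not the Fantes scale, and no comparison by arm is promised.

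Masked grading protects against grader bias. It does not recover haze already treated and cleared, or turn prevalence into incidence.

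Finally, the added comparison has low power and does not cure the null-result reading, which also rests on having no haze margin and no haze power. That is true, and is why the fix includes an explicit statement on interpretation.

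**Conclusion.** The mismatch holds on the text. The plan gives haze prevalence at each visit under usual care, after steroid changes that are not counted by arm, while the objective is incidence. It concerns a secondary outcome, but one named in the hypothesis and objective and feeding the stated reading of a null result. The repair is cheap, so it should be made.

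A reader might infer that the per-visit analysis must shrink a true difference, by the percentages in the first table. The documents do not support that. Those figures rest on one assumed onset profile and equal clearing; other profiles give 61 to 70% where even onset gives 32.5 to 47.5%, and unequal clearing can enlarge or reverse the difference. They illustrate the mechanism and are not evidence of impact. Size and direction are unknown because no haze, clearing or rescue rates are given.

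**What to change.** **Item 9.**
- Before any look at data by arm, set the masked Fantes grade that counts as visually significant. Best corrected acuity at the same visit may be used in support.
- Compare by randomised arm the proportion of patients who ever reach that level in either eye at a scheduled visit before enhancement, as a difference with a 95% CI. Report by arm how many patients have all five grades.
- Keep the per-visit grades as the treatment-policy result.
- State that the trial is not powered for haze and that a null result does not show equal prevention.

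**Item 6.** Record the date, the reason and the new drug or dose for every steroid change made for haze, including at unscheduled visits, and tabulate these by arm. Keep them out of the main comparison: the treating physician is not stated to be masked, and moving a Group 1 patient to prednisolone would count as a change while keeping a Group 2 patient on it longer would not.

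**Cost.** Three chart fields, one threshold, one table and one comparison from grades already collected; no extra visits or patients, and no change in care. The added comparison may be inconclusive, misses haze cleared between visits, and runs low where grades are missing.

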Yes No

If no, list the procedures that are performed for research purposes only (non-standard or non-standard of care procedures):

Only data collection and analysis are for research purposes only. All other procedures are within the standard of care.

8. Is there a safety monitoring plan for this study?

Yes No

9. Provide a summary of the statistical methods, data analysis, or data interpretation planned for this study. Factors for determining the proposed sample size (e.g., power) should be stated.

Standard statistics will be calculated and used to describe the two treatment groups in terms of all study variables: intraocular pressure, grade of corneal haze, manifest refraction, best corrected visual acuity, and uncorrected visual acuity. Statistics will be compiled for each variable at the study time points listed in the data collection protocol. Patients withdrawn from the study prior to surgery will not be included in the data analysis and will be replaced in the enrollment group. For eyes that require enhancement surgery, only data collected prior to the enhancement surgery will be included in the statistical analysis.

Prior studies have considered intraocular pressure elevation of greater than or equal to 10 mm Hg above baseline clinically significant. A prior study of healthy volunteers demonstrated an incidence of IOP elevation > 10 mm Hg of 1.95% in patients using loteprednol eye drops versus 7.48% in patients using dexamethasone eye drops [1]. Using these expected proportions, an alpha of 0.05, and a power of 80%, we would need a sample size of 230 patients (460 eyes). In order to account for about 10% dropout, we intend to enroll 250 patients in the study, 125 in the loteprednol arm and 125 in the prednisolone and fluorometholone arm.

IRB_00075978

Created: 8/9/2014 9:53 AM

IRB_00075978

PI: [name]

Submitted: 8/20/2014

View: 4.2 Consent Process

Title: Efficacy and safety of loteprednol 0.5% gel for routine prophylaxis after photorefractive keratectomy compared to prednisolone acetate 1% suspension and fluorometholone 0.1% suspension

Consent Process

1. The following investigators and internal staff will obtain consent (as indicated on the Study Location and Sponsors Page):

[name] University of Utah

[name]

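### A pressure rise found and treated between visits is left out of the IOP study data while later treated readings stay in, and no comparison of rescue by arm is planned

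*Combined protocol and SAP*

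**What the plan says.** All of the rules are in section 4 (Study Information) of the combined protocol and SAP.

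- **Outcome (item 6).** "The primary outcome measure will be intraocular pressure at each study time point". IOP is scheduled before surgery, at week 1 and at months 1, 2, 3, 6 and 12, and is taken by a masked technician or physician.
- **Rescue (item 6).** "Routine clinical management may be altered if the intraocular pressure is elevated sufficiently to require medical intervention"; significant haze and other complications are also grounds. In those cases "additional IOP lowering drops may be added or the steroid decreased, changed, or increased, based on the clinical picture and physician judgement". No pressure threshold is given.
- **Extra examinations (item 6).** These may be done between visits under the surgeon's "usual care, but will not be considered part of the study data".
- **Adverse events (item 6).** Any untoward occurrence from the day of surgery to the last visit goes on a study log and is detailed in the chart.
- **Analysis (item 9).** The arms are described "in terms of all study variables: intraocular pressure, grade of corneal haze, manifest refraction, best corrected visual acuity, and uncorrected visual acuity". The summaries are tied to the visit schedule: "Statistics will be compiled for each variable at the study time points listed in the data collection protocol". The only cut-off after surgery is this one: "For eyes that require enhancement surgery, only data collected prior to the enhancement surgery will be included in the statistical analysis".

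The Hypothesis expects loteprednol to do as well or better on haze "with a lower incidence of intraocular pressure elevation". The Objectives, and section 6 item 2, would take the absence of a detected difference in efficacy or safety as support for either regimen.

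**The concern.** Rescue acts directly on the primary outcome. When it starts at an examination between visits, the plan leaves out the untreated reading that prompted it and keeps the treated readings that follow. Neither rescue drops nor steroid changes are among the five variables that item 9 summarises, so the amount of treatment behind each arm's pressures would not be shown.

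What is at stake is the reading of a null result. If the comparator causes more rises, as the Hypothesis expects, and those eyes are rescued more often, later mean pressures and any count of elevations taken from scheduled readings may be drawn together. The plan would then report that either regimen is acceptable, when one of them needed more treatment to get there.

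**Working it through.** **1. Follow an eye through the rules.**

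| Situation | Prompting reading in IOP data? | Later readings in IOP data? | Rescue in a planned by-arm summary? |
|---|---|---|---|
| Rise first seen at a scheduled visit, then treated | Yes, masked | Yes, as treated | No |
| Rise found and treated between visits | No | Yes, as treated | No |
| Steroid increased for haze | Not applicable | Yes, on more steroid | No |

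The second row loses information on the primary outcome. The last column is the reporting gap, and it applies to all three rows.

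**2. Room for unseen rises.** Taking nominal visit days of 7, 30, 61, 91, 183 and 365, the gaps after week 1 are 23, 31, 30, 92 and 182 days. The documents give no taper length after week 1, so it is not known how much of the long gaps falls on steroid treatment.

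**3. The plan's own figure.** Item 9 gives rates of 1.95% (loteprednol) and 7.48% (dexamethasone) from healthy volunteers, and a requirement of 230 patients (460 eyes). The two-sided pooled formula with alpha 0.05 and 80% power is n = [1.960·√(2p̄q̄) + 0.842·√(p₁q₁ + p₂q₂)]² / (p₂ − p₁)², with p̄ = 0.04715. It gives 230 units per arm, 460 in all, so the plan's figure reproduces with eyes as the unit. The present point does not depend on it; the two rates are borrowed below only as a scale.

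**4. Illustration on mean IOP (inputs assumed).** Shift in the mean difference at a later visit = (difference in share of eyes rescued) × (mm Hg lowered). Take rescue shares equal to the plan's rates, a difference of 7.48 − 1.95 = 5.53 points.

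| Assumed lowering | All such eyes rescued | Half rescued | Equal rescue in both arms |
|---|---|---|---|
| 4 mm Hg | 0.0553 × 4 = 0.22 | 0.11 | 0 |
| 7 mm Hg | 0.0553 × 7 = 0.39 | 0.19 | 0 |
| 10 mm Hg | 0.0553 × 10 = 0.55 | 0.28 | 0 |

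For scale, a 10 mm Hg rise in those excess eyes adds 0.0553 × 10 = 0.55 mm Hg to the mean difference in the first place. Haze works differently: steroid increases in 5 points more eyes of one arm, raising IOP by 2 to 5 mm Hg, move the difference by 0.05 × 2 = 0.10 to 0.05 × 5 = 0.25 mm Hg. With the comparator running higher, that narrows it if the excess is in the loteprednol arm and widens it if in the comparator arm.

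**5. Illustration on the count of elevations (hidden shares assumed).** If shares m_C and m_L of rises in the comparator and loteprednol arms are treated between visits and never appear at a scheduled one, the visible difference is 7.48(1 − m_C) − 1.95(1 − m_L) points.

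| Hidden share | Equal in both arms | Comparator only | Loteprednol only |
|---|---|---|---|
| 0 | 5.53 | 5.53 | 5.53 |
| 25% | 4.15 | 5.61 − 1.95 = 3.66 | 7.48 − 1.46 = 6.02 |
| 50% | 2.77 | 3.74 − 1.95 = 1.79 | 7.48 − 0.98 = 6.50 |

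The difference can narrow or widen, depending on where rescue falls. The documents give neither a rescue rate nor a hidden share.

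**The case against.** The strongest defence is that the plan compares two regimens under routine care, with pressure taken by masked staff at fixed times. Adding readings from examinations done at the surgeon's discretion would bring in uneven and possibly unmasked ascertainment. That stands. It is the reason to keep the general exclusion and to keep as-managed IOP as the main summary. It does not answer why the one reading that triggered treatment should be lost, or why rescue should go unreported.

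Second, a reader might infer that rescue itself is barred from the study data, or goes unrecorded. The text does not say so. It excludes the extra examinations, not the treatment, and a rise needing treatment fits the adverse event definition. Rescue is therefore probably recoverable. What is missing is a planned summary by arm and a link to the IOP results. Item 9 is only a summary of methods, so silence there does not prove that no adverse event table will be made; but nothing commits the trial to one.

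Third, the mm Hg figures lie towards the upper end of what the borrowed rates would allow. They use dexamethasone rates in healthy volunteers, treat an incidence as the share still under rescue at a single visit, and ignore the fall that tapering would bring anyway. This is correct, and they should not be used as estimates.

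Fourth, the sensitivity analysis proposed below has no main incidence analysis in item 9 to set it against. That is a fair limit. The Hypothesis, Objectives and sample size are all framed as incidence, however, and showing the components separately makes the scheduled rises of at least 10 mm Hg visible alone.

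**Conclusion.** The point holds as a matter of data handling. Followed as written, the plan omits from the IOP data a rise found and treated between visits, keeps the treated readings that follow, and commits to no comparison of rescue by arm. Rises first seen at a scheduled visit are kept, so the loss is confined to those found in the gaps. Later treated readings enter in both cases.

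A reader might go further and infer that the result is biased towards no difference by a known amount. The documents do not support that. Narrowing requires more IOP-driven rescue in the arm with the higher pressure; equal rescue shares and equal lowering leave the mean difference unchanged, and haze-driven steroid increases can act either way. The 0 to 0.55 mm Hg range rests on assumed rescue shares and assumed treatment effects. The point deserves a change because the plan would read a null result as support for either regimen, and because the missing information is cheap to collect.

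**What to change.** **Item 6.** Keep the exclusion of unscheduled examinations, with one exception: the IOP reading that prompted IOP-lowering treatment. From the chart and adverse event log, record for each eye any IOP-lowering drops, and any steroid change with a documented IOP or haze reason, with the start date. A documented reason is needed because both arms taper on clinical judgement, so a departure from the taper cannot otherwise be recognised.

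**Item 9.**
1. State that by-visit IOP is as observed under the regimen as managed, rescue included.
2. Report by arm and visit the patients and eyes with IOP-lowering drops, with IOP-driven steroid changes and with haze-driven steroid changes, on separate lines.
3. Add a patient-level sensitivity analysis of any of: a rise of at least 10 mm Hg above baseline at a scheduled visit; such a rise at an unscheduled examination that prompted treatment; or the start of IOP-lowering drops. Show the components separately. The patient is the unit because the patient is randomised and both eyes receive one regimen.

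**Cost.** A few chart-derived fields and a few sentences; clinical care does not change. If the plan's rates applied, the IOP-driven cases would be about 115 × 0.0748 = 8.6 and 115 × 0.0195 = 2.2 patients, roughly 9 against 2 of 115 per arm. Haze-driven changes come on top, in a number that the documents do not give. The downside is that starting drops, and which unscheduled readings prompt treatment, depend on a physician not stated to be masked. That physician might treat earlier on prednisolone and so favour the Hypothesis, which is why this stays a sensitivity analysis.
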